### **3) Analysis populations.**

- a. **Intention-to-treat.** The primary analysis will be intent to treat (ITT). The ITT analysis will include all participants in both arms who were enrolled and completed all baseline assessments, regardless of if they received the

- intervention or not.
- b. **Per protocol.** A secondary analysis will be per-protocol, including control participants with baseline and follow-up evaluations who did not have any major protocol violations, and intervention participants with baseline and follow-up evaluations who adhered to the intervention (i.e., attended at least the first individual counselling session, 2 out of 4 group education sessions, and received at least 60% of weekly food allotment), and no major protocol violations.

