## 2) Adherence and protocol deviations

- a. **Definition of exposure to the intervention and how this is assessed including extent of exposure:**

Adherence to the intervention will be assessed through the following mechanisms:

- i. Counseling: Attends at least the first individual counseling session (out of 2)
- ii. Group education: Attends at least 50% of group education sessions (2 out of 4).
- iii. Food: Receive at least 60% of weekly food allotment.

- b. **Description of how adherence to the intervention will be presented – We**  
will Adherence to the intervention will be presented through a brief description in

the narrative summarizing the percent of weekly engagement with food deliveries/pickups,  
% of food allotments received, and % of food reported eaten, as well as % of counseling sessions and education sessions attended.

c. **Protocol deviation.** The following are pre-defined minor protocol violations:

- i. Participants that for any reason are not seen within the visit window (up to two months later).
- ii. Investigators miss giving a questionnaire or a section of the questionnaire to the participant, including the dietary recall questionnaire.
- iii. Investigators miss recording or performing any anthropometric / blood pressure evaluations or blood draw or done outside of visit window.

The following are pre-defined major protocol violations:

- i. Participants that are mistakenly enrolled in the study without meeting the inclusion criteria.
- ii. Participants in the control arm receiving meals or groceries from Project Open Hand during the active intervention period (baseline to 6 months).
- iii. Participants for whom informed consent was not obtained prior to any study- specific tests/procedures.
- iv. Lapse in study approval

The number (and percentage) of participants with major and minor protocol deviations will be summarized by arm with details of type of deviation provided. The participants that are included in the ITT analysis data set will be used as the denominator to calculate the percentages. No formal statistical testing will be undertaken.

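### The secondary per-protocol comparison selects on adherence in the intervention arm only, so it can be biased towards benefit and should not be read as a causal effect

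*Combined protocol and SAP*

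**What the plan says.** Section 4, 3) Analysis populations makes intention to treat the primary analysis and adds: "A secondary analysis will be per-protocol". The two arms enter that second set by different rules.

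- Control arm: "control participants with baseline and follow-up evaluations who did not have any major protocol violations".
- Intervention arm: "intervention participants with baseline and follow-up evaluations who adhered to the intervention", with no major violation. Adherence means that the person "attended at least the first individual counselling session, 2 out of 4 group education sessions, and received at least 60% of weekly food allotment".

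Section 4, 2) Adherence and protocol deviations gives the same thresholds, for example "Food: Receive at least 60% of weekly food allotment". The major violation specific to controls is "Participants in the control arm receiving meals or groceries from Project Open Hand during the active intervention period". That measures contamination. It says nothing about how engaged a control participant is.

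Section 6, 2) Analysis methods regresses change in the outcome on its baseline value and arm. Propensity or doubly robust methods come in only if the arms differ at baseline, and a further analysis adjusts for medication use. Neither is tied to the per-protocol set or to adherence. Section 6, 3) Sensitivity analysis rules out anything further.

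**The concern.** Attending classes and collecting food week after week is behaviour observed after randomisation. Section 2 of the plan itself links non-adherence and missed clinic visits to worse diabetes outcomes, and Aim 2 treats medication adherence, self-management and clinic attendance as routes to glycaemic control. If the people who meet all three criteria are also stronger on those behaviours, the intervention side of the comparison is enriched for good prognosis and the control side is not. Illness can act the same way: a participant who falls ill may miss classes and food and leave the set, while an equally ill control who attends follow-up stays in. Adjusting for baseline HbA1c does not remove such differences.

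This is the plan's only between-arm estimate restricted to people who took up the programme, and Section 4, 1) would report it with a 95% confidence interval and a p-value. It would carry most weight with readers when the intention-to-treat result is weak. Nor is it limited to HbA1c: for missed visits or medication adherence, the filter selects on behaviour close to the outcome itself.

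**Working it through.** **Inputs from the documents.** SD of HbA1c change 1.3937 and minimum important difference 0.5 (Section 3, 5) Sample size); 20% anticipated attrition (same section); 156 intervention and 125 control participants (Section 7).

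**Inputs assumed.** The share p of followed-up intervention participants who meet all three criteria, and the correlation r between adherence propensity and favourable HbA1c change. The documents give neither. The true effect is set to zero.

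**The plan's own figure first.** One-sided 5%, 80% power: n per arm = 2 × (1.645 + 0.842)² × 1.3937² / 0.5² ≈ 96.1, so 97, against 98 stated. With the t distribution, power is 80.1% at 97 and 80.4% at 98. Then 196 / 0.8 = 245, as stated. The SD and difference are therefore usable as given. The plan states no figure for the per-protocol set.

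**Numbers followed up.** 156 × 0.8 ≈ 125 intervention; 125 × 0.8 = 100 control.

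**Expected contrast under no effect.** If adherers are the upper fraction p of a normal propensity score, their mean change differs from that of the whole arm by

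bias = r × SD × φ(z_p) / p,

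where z_p is the p quantile and φ the density of the standard normal. The factor φ(z_p)/p is 0.798 at p = 0.5, 0.644 at 0.6 and 0.497 at 0.7. For example, 0.3 × 1.3937 × 0.798 = 0.334 and 0.1 × 1.3937 × 0.497 = 0.069.

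Spurious benefit in HbA1c points (negative means towards harm). In brackets is the chance that a 95% interval excludes zero on either side, allowing for the smaller variance among adherers:

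| r | p = 0.5 | p = 0.6 | p = 0.7 |
|---|---|---|---|
| -0.1 | -0.111 (7.9%) | -0.090 (7.1%) | -0.069 (6.3%) |
| 0 | 0 (5%) | 0 (5%) | 0 (5%) |
| 0.1 | 0.111 (7.9%) | 0.090 (7.1%) | 0.069 (6.3%) |
| 0.2 | 0.222 (16.9%) | 0.179 (13.6%) | 0.138 (10.5%) |
| 0.3 | 0.334 (32.7%) | 0.269 (25.0%) | 0.208 (17.8%) |

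Without the variance reduction, SE = 1.3937 × √(1/(125p) + 1/100), which is 0.225 at p = 0.5 and 0.204 at p = 0.7. The highest rate is then 31.7% instead of 32.7%. Higher adherence shrinks the problem: at r = 0.3 the bias is 0.146 at p = 0.8 and 0.082 at p = 0.9.

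**Simulation check**, 20,000 trials per scenario, p = 0.6, no true effect:

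| r | Point estimate favours intervention | 95% interval excludes zero in its favour |
|---|---|---|
| -0.1 | 33% | 0.9% |
| 0 | 50% | 2.7% |
| 0.2 | 80% | 13% |
| 0.3 | 90% | 25% |

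**The same bias without a correlation.** If adherers would do better than non-adherers by D points without treatment, bias = (1 − p) × D. With p = 0.6 and D = 0.5 this is 0.4 × 0.5 = 0.20, or 40% of the minimum important difference.

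**The case against.** A reader might infer that the per-protocol analysis will show a benefit even if the programme does nothing. The documents do not support that. They give no adherence rate and no prognostic gap, and the table includes zero and negative bias. Greater need may drive food uptake: Section 2 ties food insecurity to poor glycaemic control, and Section 3, 2) offers home delivery to non-mobile people. Even at p = 0.6 and r = 0.3, only about a quarter of null trials would give an interval excluding zero in the intervention's favour.

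A reader might also infer that the trial's main conclusion is at risk. It is not, because intention to treat is primary. Section 4, 2) also commits to reporting actual uptake, and Section 4, 1) plans no significance testing unless a journal requires it.

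There are partial mitigants. Controls must also have a follow-up evaluation. Before randomisation, Section 5, 2) excludes people who cannot attend workshops or cannot schedule baseline assessments, which narrows the spread of engagement. The planned model conditions on baseline, so if r is the correlation left after that adjustment, the relevant SD is below 1.3937 and the bias in points is smaller.

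All of this limits certainty and size. None of it restores comparability: the mitigants are incomplete, the additional adjustments are not tied to this population, and secondary status does not make a selected contrast a causal estimate.

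**Conclusion.** The concern holds in a limited form. The selection rule is asymmetric, it acts after randomisation, and the plan does nothing to correct for it. That much rests on the text alone. The direction and size rest on assumptions. Bias towards benefit is likely if adherers have the better prognosis, which the plan's own conceptual model makes plausible but does not quantify. For 50-70% adherence and a correlation of 0 to 0.3, the spurious HbA1c benefit is 0 to about 0.33 points, at most two-thirds of the minimum important difference. At a correlation of -0.1 it is about 0.07 to 0.11 towards harm. The intention-to-treat conclusion stands either way. What should change is how the per-protocol estimate is labelled, and which analysis answers the question about uptake.

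**What to change.** Two changes to the SAP.

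1. State in Section 4, 3) b that the per-protocol contrast is descriptive and does not estimate a causal effect.
2. Make the secondary estimate of the effect of uptake a complier-average effect by two-stage least squares. Use randomised arm as the instrument, the same baseline-adjusted model, and every participant with a six-month outcome. Define treatment received on the whole package: any uptake of Project Open Hand food, counselling or classes, with the three-criterion adherence definition as a variant. Count control participants who received the package as treated. Interpret the result as the effect of the package.

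Food received should not be the sole treatment variable. Section 3, 2) describes a programme of food, individual counselling and group classes, so a food-only model would credit any effect of the education to the food.

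The cost is SAP wording and one extra regression. Project Open Hand supplies weekly food records for each participant (Section 3, Data collection, item h), and the plan already commits to reporting session attendance. The statistical price is a wider interval: the SE is about 1/f times that of intention to treat, where f is the between-arm difference in uptake (1/0.7 ≈ 1.4; 1/0.5 = 2). The method also assumes that assignment affects outcomes only through uptake. That assumption is weaker for any uptake than for the three-criterion cut-off, because partial adherers may benefit too. Loss to follow-up is left as it is in the primary model.

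Section 3, 8) Timing of final analyses planned analysis from March 2025. If it has begun, label the added estimate post hoc and still report the caveat on the per-protocol contrast.

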## Section 5: Trial Population

### 1) Screening Data

- a. Participants will be recruited primarily from safety-net clinics serving low-income individuals in geographic areas of San Francisco and Alameda County.
- b. Participants will be recruited through community clinics in one of following ways: 1) Providers and staff at the clinic will refer adults with T2DM confirmed with medical or laboratory records to the CHEFS-DM study using an outreach script provided by research staff; 2) Recruitment flyers will be posted in clinics and waiting areas and at various community sites such as senior centers; individuals with T2DM can then contact the study coordinator directly through the contact information listed on the flyers; 3) research staff will be available in clinic to discuss the study opportunity with patients and conduct eligibility screening. Research staff will then conduct phone outreach to assess for eligibility and interest in participating.  
UCSF will screen patients either over the phone or in-person for eligibility based on study inclusion and exclusion criteria using the study recruitment script and by reviewing the diabetes diagnosis, HbA1c test date and result provided by a study clinic or managed health care plan partner, and by noting whether the individual is a current or past Project Open Hand client.  
A summary will be provided indicating the number of participants screened, number of participants eligible, number of participants not eligible and reason for non-eligibility, number of participants enrolled, number of participants not enrolled and the reason for non-enrollment, and the number of participants randomized. This summary will be provided overall, and by location (i.e., San Francisco or Alameda county).

### 2) Eligibility – summary of eligibility

criteria Inclusion Criteria:

1. Confirmed diagnosis of T2DM confirmed by medical or laboratory records. For T2DM, the criteria (from the American Diabetes Association) are glycated hemoglobin (HbA1c)  $\geq 6.5\%$ , or fasting plasma glucose of  $\geq 126$ , or a 2-hour plasma glucose level of 200 or higher during a 75 g oral glucose tolerance test, or a random plasma glucose of 200 or higher in patients with symptoms of hyperglycemia.
2. Age  $\geq 18$  years.
3. Screening positive for food insecurity (at least one positive question) in the previous 6 months assessed using the 6-item version of the US Household Food Security Survey Module (US Department of Agriculture) or has household income  $<200\%$  of the federal poverty level.
4. English or Spanish language fluency.
5. Adequate cognitive and hearing capacity to consent and complete study measures.
6. Reside in Alameda County or San Francisco County.

Exclusion Criteria:

1. Type-1 diabetes mellitus
2. Individuals with disorders known to affect the accuracy of the HbA1c measure (e.g., end stage renal disease and individuals with known hemoglobinopathies).
3. Inability to attend the educational workshops.
4. Inability to schedule baseline assessments and/or blood draw after repeated requests.
5. Pregnant individuals, or individuals planning to get pregnant within 6 months, or are lactating, or are postpartum less than 6 months.
6. Current POH clients, past POH clients who stopped services less than 6 months prior, or past or present participants in other POH medically tailored meals studies.
7. Does not have access to food storage, including a refrigerator and freezer to safely keep food.
8. Does not have access to facilities to reheat and prepare meals using

Project Open Hand food.

9. Anticipates moving out of study area of Alameda and San Francisco Counties in the next 6 months.
10. Receives more than 1 meal per day from a free food support resource or agency.
11. Allergic to or will not eat eggs, soy, wheat, nuts, seeds or seed oils, or other foods commonly included among ingredients in POH meals.
12. Allergic to dairy products, or unable to tolerate any dairy products including milk, yogurt, and cheese.
13. Individual does not eat any or all of POH's meat meal options and will not eat the vegetarian POH meal option.

3) **Recruitment** – A CONSORT flow diagram will be used to summarize the number of participants who were:

- a. Assessed for eligibility at screening
  - i. Eligible at screening
  - ii. Non eligible at screening, and reasons why were not eligible
- b. Eligible and randomized
  - i. Eligible and randomized
  - ii. Eligible but non-randomized, and reason
- c. Lost to follow up at six months, and reason
- d. Lost to follow up at twelve months (intervention arm), and reason
- e. Discontinued the intervention, and reason
- f. Randomized and included in primary analysis
- g. Randomized and excluded from the primary analysis, (if any), and reason.

4) **Withdrawal/follow-up**

Reasons and details of withdrawal at 6 months for both arms, and at 12 months for intervention arm will be reported. This information will be summarized in the CONSORT flow diagram. In addition, the numbers of losses to follow up will be summarized by treatment arm.

5) **Baseline patient characteristics.**

- a. **List of baseline characteristics to be summarized.** Sociodemographic and clinical characteristics at baseline overall and by study arm will be described.

These characteristics includes age, sex, household size, educational attainment, income, housing situation, relationship status, language(s) spoken, household food insecurity, employment status, health-related quality of life, health care utilization, mental health (depressive symptoms score, diabetes distress scale, behavioral (diabetes medication adherence, diabetes self-management, clinic attendance, diet quality, substance use), and clinical outcomes at baseline (HbA1c, blood pressure, BMI, cholesterol).

b. **Details of how baseline characteristics will be descriptively summarized.**

Categorical variables will be presented as numbers and percentages. Continuous variables will be summarized by mean and SD for variables with normal distribution, and by median and IQR if data are skewed. Minimum and maximum values will also be presented for continuous data. Tests of statistical significance will not be performed for baseline characteristics.

## Section 6: Analysis

### 1) **Outcome definitions**

Primary Outcome Measures:

1. Hemoglobin A1c. At baseline and six months, all participants will undergo the blood draw; at twelve months, the blood draw will be implemented in the intervention arm only. The change on HbA1c from baseline to six months by study arm will be reported.
2. Food security. Food insecurity will be measured with the adult version of the USDA Household Food Security Survey Module (HFSSM), validated in many populations. The score ranges from 0 to 10 . Higher scores indicates higher severity of food insecurity. The change in the food insecurity scores from baseline to six months by study arms will be reported.

Secondary Outcome Measures:

1. Glucose control. The change in the proportion of participants with glucose control, defined as HbA1c <9%, from baseline to six months by study arms will be reported.
2. Low food security. Food security as a binary response will be assessed, identifying a participant having low or very low food security or food security (food security or marginal food secure) by study arm.

3. Systolic and diastolic blood pressure. Changes in the average of three repeated measurements of systolic and diastolic blood pressure (mmHg) from baseline to six months by study arm will be reported.
4. Medication adherence. A Single-Item Rating Visual Analogue Scale (range 0-100) for medication adherence will estimate the percentage of medications taken in the past month and is reliable and valid, including in low-literacy populations. The change in medication adherence (percentage points) from baseline to six months between intervention and control arms will be reported.
5. Acute care utilization. Information on acute care utilization (emergency department and urgent care) by self-report and/or medical record review will be collected. The proportion of participants that used acute health care from baseline to six months by study arm will be reported.
6. Hospitalization. Information on hospital admissions will be collected by self-report and/or medical record review. The proportion of participants with at least one event of hospitalization will be reported by study arm.
7. Missed outpatient visits. Information on missed outpatient visits will be collected by self-report and/or medical record review. The proportion of participants that missed at least one outpatient visits from baseline to six months will be reported.
8. Health-related quality of life (HRQL). The standardized 12-item short form health survey will be used to measure the HRQL. The SF-12v2 provides a summary score for physical and mental health. The transformed *T* score has a mean=50 and SD=10, in which higher values means better health. The change in SF-12 *T* scores from baseline to six months by study arm will be reported
9. Body Mass Index (BMI). The average of three repeated measurements of weight and height will be obtained at baseline and at six months. The BMI will be calculated (weight (kg)/ (height (m)). Changes in in BMI values (kg/ m^2) from baseline to six months by study arm will be reported.
10. Diet quality. Dietary information using an automated self- administered 24-hour dietary recall instrument from the National Cancer Institute's (ASA24) will be collected. The HEI-2015 is a measure of diet quality which evaluates how well the food consumed aligns with the Dietary guidelines for American population. The HEI-2015 score ranges from 0-100 in which a higher score indicates better diet quality. The adequacy component of the HEI ranges from 0-60 and the moderation component ranges from 0-40 (both with higher score indicating better diet quality). Changes in the adequacy and moderation HEI-2015 scores from baseline to

six months by study arm will be reported.

11. Depressive symptoms. Symptoms corresponding to the Diagnostic and Statistical Manual of Mental Disorders will be measured using the 9-item Patient Health Questionnaire (PHQ-9), a reliable and valid measure of symptom severity. The PHQ-9 score ranges from 0 to 27, with higher scores indicating higher levels of depression. The change in PHQ-9 scores from baseline to six months among by study arms will be reported.
12. Diabetes distress scale. The diabetes distress scale (DDS) has 17 items measuring frustration, anger, and discouragement associated with managing complex diabetes healthcare directives. The DDS score ranges from 1 to 6, with higher scores indicating higher levels of distress. The change in diabetes distress scores from baseline to six months by study arms will be reported.
13. Diabetes self-efficacy. The 8-item Perceived Diabetes Self-Management (PDSM) scale, which assesses confidence in one's ability to manage numerous self-care behaviors, including diet and glucose management will be used. The PDSM scores ranges from 8 to 40, with higher scores indicating more confidence in self-managing their diabetes. The changes in the PDSM scores from baseline to six months by study arm will be reported.

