- d) Blood draws (baseline, 6, and 12 months): Participants will undergo a blood draw (testing a lipid panel, and HemoglobinA1c) at one of 28 Quest Diagnostics labs in San Francisco or Alameda counties Phlebotomy will be performed using universal precautions. Date and time of phlebotomy, and specimen number will be recorded in a participant log. Specimens will be aliquoted and stored at -70°C using standard universal precautions. Data will be received from Quest Diagnostics in the form of a spreadsheet which can be easily merged with other study data by participant ID or will be accessed by UCSF staff using the secure Quest Diagnostics HIPPA-compliant online portal. At baseline and six months, all participants will undergo the blood draw; at twelve months, the blood draw will be implemented in the intervention arm only.
- e) 24-hour Dietary Recall (baseline and 6 months). Dietary intake will be assessed via 24-hour dietary recalls by UCSF RA trained by registered dietitians using the National Cancer Institute's Automated Self- Administered 24-hour Dietary Recall (ASA24). Participants will complete two unannounced recalls (one weekday and one weekend day) during a one-week period. In total, participants will complete four recalls: 2 at baseline and 2 at 6-month follow- up. RA's will inform the participant of which week the calls will be attempted. Previous work has indicated that lower income or older adults may need additional assistance with completing the ASA24, therefore the questions will be administered over the phone or in person (if COVID permits), using strategies to ensure the collection of dietary data is accurate and does not burden the participant. The 24-hour dietary recall will be conducted at baseline and six-month follow up.
- f) Medical record review (baseline, 6, and 12 months). Medical records will be used

during recruitment to confirm T2DM diagnosis, to confirm participant HbA1c, preferentially greater than or equal to 6.5%, and to determine whether a patient has controlled or uncontrolled T2DM using latest HbA1C test result. Medical record review is also being used to collect follow-up HbA1c data if completing a blood draw is not possible during follow-up, if medical record A1c is available within the assessment time frame, and with the consent of the participant.

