#### 4) Randomization

281 participants were randomized 1:1 to the intervention and control arms,

stratified by county (San Francisco vs. Alameda County) and poor diabetes control (A1c < 9%, vs.  $\geq$  9%). Details of the randomization and stratification method is stored securely in REDCap. Randomization based on a computer-generated assignment will occur after the participant has provided informed consent and completed baseline assessments.

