## 2) Analysis methods

- a. **Preliminary/Descriptive analyses.** Frequency tables for all variables and measures of central tendency and variability for continuous variables will characterize the sample and be stratified by randomization arm to check for non-equivalence. If the two arms differ at baseline on any covariates, the Rubin causal model (e.g., propensity scores, double- robust estimation) will be used to obtain the desired marginal effect estimates under the counterfactual assumption of balanced arm. Although the computerized data collection protocol and the presence of an interviewer should minimize missing data, the analyst will examine patterns of non-response, and inspect distributions of mediating and outcome variables to identify outlying or unusual values and assess distributional characteristics. Validity and reliability of scale constructs via confirmatory factor analysis and internal consistency will be verified.

**Analyses for Aim 1 (Diabetes and other clinical health outcomes):** The intervention is intended to improve clinical outcomes suggested by our intervention model. Specifically, the hypothesis is that the CHEFS-DM intervention will lead to improved (i.e., lower) mean HbA1c (primary outcome). For the primary analysis,

an intent-to-treat analysis of covariance will be done using the Stata regress and/or sem procedure with the primary outcome being changes from baseline to six months. The data for this analysis will be constructed in wide form, i.e., with an individual being a row in the data and the columns being the variables from both baseline and six months. The model will regress the change in an outcome variable on the baseline value of that outcome and arm (intervention or control). The model will be estimated by least-squares when using the regress procedure. Additional analyses will be done to a) check robustness if the two arms differ at baseline by controlling for the propensity score (or the covariates that were important in the propensity score); and b) adjust for medication use. If covariates have missing data, the sem procedure will be used with full information maximum likelihood to incorporate all covariate data under the assumption that missingness is at random.

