### 4) Subgroup analysis

- a. Additional models and statistical interactions (i.e., product terms) will be performed to identify characteristics of individuals who most benefitted from the intervention, such as East Bay versus San Francisco, sex, race/ethnicity, food insecurity, poor T2DM control ( $A1c \geq 9$ ), and insulin use.

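### Secondary outcome 1 (HbA1c <9%) would be adjusted only for a yes/no baseline although continuous baseline HbA1c is collected; the 9% subgroup test also needs a continuous companion

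*Combined protocol and SAP*

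**What the plan says.** - **Outcome.** Section 6, 1) Outcome definitions, secondary outcome 1: "The change in the proportion of participants with glucose control, defined as HbA1c <9%, from baseline to six months by study arms will be reported".
- **Model.** Section 6, 2) Analysis methods, Aim 1: "The model will regress the change in an outcome variable on the baseline value of that outcome and arm (intervention or control"). The same section applies similar linear or logistic analyses to the secondary outcomes. It names no different baseline covariate for the binary ones.
- **Subgroups.** Section 6, 4) Subgroup analysis plans product terms "to identify characteristics of individuals who most benefitted from the intervention". Its examples include "sex, race/ethnicity, food insecurity, poor T2DM control ( $A1c \geq 9$ ), and insulin use".
- **Randomization.** Section 3, 4) Randomization: allocation was "stratified by county (San Francisco vs. Alameda County) and poor diabetes control", with the cut at A1c 9%.
- **Other checks.** Section 6, 3) Sensitivity analysis adds nothing to what is described elsewhere.

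**The concern.** For the primary outcome, the baseline value of the outcome is HbA1c on its continuous scale. For secondary outcome 1, the same rule gives an indicator of HbA1c below 9%. Everyone below 9% then carries one covariate value, whether far below the cut or just under it, although their chances of being below 9% at six months differ widely. The model ignores prognostic information that the trial has already collected, so the arm comparison on this outcome is less efficient than it could be.

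The subgroup section raises a related question. Diabetes control appears as a moderator only in its 9% form. If benefit rises gradually with baseline HbA1c, a single cut is a blunt way to detect it, and no continuous version is prespecified. At stake are the efficiency of one secondary outcome and the interpretation of one exploratory moderator.

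**Working it through.** **1. The plan's own figures.** Section 3, 5) Sample size uses an SD of change of 1.3937, a difference of 0.5, one-sided alpha 0.05 and 80% power.

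n per arm = 2 × (1.645 + 0.842)² × (1.3937 / 0.5)² = 2 × 6.18 × 7.77 ≈ 96.1, so 97 per arm or 194 in total. The plan's 196 agrees within rounding, and 196 / 0.8 = 245 matches its recruitment figure. For 0.36 versus 0.20 the same approach gives 97 per arm. These figures are not in dispute.

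**2. Inputs for the check.**
- From the documents: SD of change 1.3937; effect 0.5; arms of 156 and 125 (Section 7); 20% attrition. Analysed: 156 × 0.8 ≈ 125 and 125 × 0.8 = 100.
- Assumed, because the documents give no figures: baseline HbA1c follows a shifted gamma distribution, with mean 7.5 to 8.7% and SD 1.5 to 2.0 across scenarios. Follow-up is regressed on baseline with slope 0.7. Residual SD = √(1.3937² − (0.3 × baseline SD)²).

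**3. What the yes/no covariate hides.** Take baseline mean 8.0 and SD 2.0, so residual SD = √(1.942 − 0.360) = 1.258. For a control participant:
- Baseline 6.2%: expected follow-up 8.0 + 0.7 × (−1.8) = 6.74. P(<9%) = Φ(2.26 / 1.258) = 0.96.
- Baseline 8.9%: expected follow-up 8.0 + 0.7 × 0.9 = 8.63. P(<9%) = Φ(0.37 / 1.258) = 0.62.

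Both carry the same covariate value.

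**4. Power for HbA1c <9% at six months (logistic model).**

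*Uniform effect of 0.5, two-sided 0.05, baseline mean 7.8 to 8.7%, SD 1.6 to 2.0.* With 1,000 runs per scenario, power is 37–42% with the yes/no baseline and 42–48% with continuous baseline HbA1c. A repeat gave 36–44% and 40–49%. Type I error was near 5% either way.

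*Benefit rising linearly above 6.5% and averaging 0.5, one-sided 0.05, 3,000 runs per scenario, both models fitted to the same simulated data:*

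| Baseline mean, SD | Yes/no baseline | Continuous baseline | Gain (points) |
|---|---|---|---|
| 7.5, 1.5 | 79.0% | 80.7% | 1.7 |
| 8.0, 1.5 | 73.4% | 75.6% | 2.2 |
| 8.0, 2.0 | 74.9% | 79.3% | 4.4 |
| 8.5, 2.0 | 67.0% | 71.7% | 4.7 |

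Together the gain is about 2 to 6 points.

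**5. Subgroup interaction (two-sided 0.05, same numbers analysed).**

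| Assumed pattern of benefit | Continuous interaction | Interaction at 9% |
|---|---|---|
| Grows by 0.35 per 1% of baseline HbA1c | 87–98% | 69–89% |
| Linear above 6.5%, averaging 0.5 | 71–90% | 51–69% |
| Step: 1.25 at ≥9%, 0.25 below | 40–60% | 60–81% |

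Repeat runs gave 84–98% against 65–91% for a linear gradient, and 41–61% against 57–81% for a step. In the second row, adding continuous baseline as a main effect raises the 9% column to 54–76%. The ranking reverses with the shape of the effect.

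**The case against.** The strongest reply is that little depends on this. The primary analysis uses continuous HbA1c change with continuous baseline HbA1c, and secondary outcome 1 is a companion summary of the same measurement. Section 4, 1) plans confidence intervals and exact p-values, with no significance testing unless a journal requires it. The outcome also stays weak after the change. Under assumed baseline means of 7.5 to 8.5% and SDs of 1.5 to 2.0, 67–85% of participants already start below 9%, and a uniform 0.5-point effect moves the proportion by only 0.06–0.10, against the 0.16 in the sample size section. All of this stands, and it limits the weight of the point. It does not justify discarding a covariate already in hand.

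A reader might infer four stronger things that the documents do not support.

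- *The missing HbA1c floor is the cause.* Eligibility indeed sets no current minimum: it asks for "Confirmed diagnosis of T2DM confirmed by medical or laboratory records", and recruitment uses records "to confirm participant HbA1c, preferentially greater than or equal to 6.5" percent. But a 6.5% floor would still pool 6.5% with 8.9%. The loss comes from the cut.
- *The 9% split should become descriptive only.* It is a randomization stratum, so it is a natural prespecified subgroup, and it has more power if benefit steps at 9%. The subgroup list is also given as examples, so a continuous interaction is unspecified but not excluded.
- *The logistic model cannot be fitted, because change in a yes/no outcome takes the values −1, 0 and 1.* The sample size section already frames binary outcomes as a proportion at follow-up, and the analysis section lets the model type vary. One clarifying sentence is enough.
- *Continuous HbA1c can never enter the model.* The plan's additional analyses may adjust for covariates if the arms differ at baseline. That is conditional, so it does not replace a stated covariate.

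**Conclusion.** The point holds as a modest efficiency improvement to one secondary outcome. As written, HbA1c <9% would be adjusted for baseline <9% yes/no, at a cost of about 2 to 6 points of power. That size rests on the assumed baseline distribution, the 0.7 slope and 20% attrition. The direction follows from the text, because the continuous value is prognostic and is left out. The sample size is not affected.

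For the subgroup analysis, the supported conclusion is narrower: a continuous interaction should be prespecified beside the 9% one. The documents do not say whether benefit is graded or steps at 9%, so neither form can be called the better test in advance.

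**What to change.** 1. **Section 6, 1) and 2), secondary outcome 1.** State that the dependent variable is HbA1c <9% at six months, fitted by logistic regression on arm and continuous baseline HbA1c. Report the standardised risk difference as well, because the adjusted odds ratio is conditional on baseline HbA1c and does not translate directly into a difference in proportions.
2. **Section 6, 4) Subgroup analysis.** Keep the interaction at A1c ≥9%. Add a prespecified interaction of arm with continuous baseline HbA1c, linear first, with a spline as the non-linearity check. Label both exploratory.
3. **Source of the value.** Say whether the subgroup uses the study baseline blood draw or the medical-record result, since Section 3, Data collection, item f uses the record to classify control at recruitment.

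The cost is SAP wording, because the data are already collected. The downside is one more exploratory test and one more effect measure to report. Version 2 is dated 02/05/2025 and analysis was planned from March 2025. The change should therefore be dated, and if outcome data by arm have already been seen, described as made afterwards.
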